In order to obtain random samples, park user and household interview respondents are recruited according to established protocols. Park users are recruited according to set quotas aimed at gaining participants equally distributed by gender, activity level, and age. Household respondents are recruited using a random selection of residential addresses. Recruitment protocols for both interview types can be found in appendices F and G.

Data collectors will obtain oral consent (appendix H) prior to administering the interview, and provide a small incentive upon completion. They also will have available a project summary sheet (in English and Spanish) that lists the project managers contact information if respondents request additional information (appendix I). If a respondent appears in need of immediate mental health services, data collectors will provide contact information for appropriate emergency services (appendix J) and inform park staff.

Park Use Counters

The 12-button age/activity counter app is designed to capture the number of park users by physical activity level and age group, i.e., observers will record physical activity and age group simultaneously for each individual park user within a defined target area. The app is for counting purposes only and the data must be entered into a separate Pendragon form described below.

The counter consists of 12 buttons arranged in four columns (age group) and three rows (activity level). Buttons are color coded by age group.

[figure not shown]
On the bottom of the app screen are summary and other functions including:

1. Observation Count: Returns a summary of the current counts.
2. Reset Counters: Returns all fields to a 0 value.
3. Edit Previous Record: Allows the observer to edit the immediately preceding entry.

[figure not shown]
Installation on an iPad

These instructions are for an iPad running iOS 7, and may be different for other devices or operating system. Safari was used to load the counters and the bookmarking and icon creation process described here may vary in other browsers.

1. Connect the device to a wireless network.
2. Open Safari on the device and navigate to <http://mmicdata.rand.org/parkcounter>.
3. Tap the 'Age/Activity' tab.

4. After arriving to the counter screen, tap the save icon on the toolbar, and choose “Add to Home Screen.” This will install the icon on the home screen.

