| Adult sport league |  Yes |  No |
| Dance classes |  Yes |  No |
| Fitness / aerobics class |  Yes |  No |
| Organized walks / hikes |  Yes |  No |
| Park events (e.g., fair) |  Yes |  No |
|  Other _____ | | |

23. What is the nearest intersection to your home?

(INTERVIEWER NOTE: Please indicate complete street name (i.e., 49th Place or 49th Street). Also verify that these streets intersect!)

Major Street _____

Cross Street _____

24. Using the map provided, indicate in which buffer the respondent's home is located.

- 0 - ¼ mile ½ - 1 mile
 ¼ - ½ mile 1+ miles

25. How long have you lived at your current address? (Check one)

- Less than 1 year
 1 - 2 years
 > 2 years, but < 5 years
 Between 5 - 9 years
 10 years or more

INTERVIEWER TO READ: Because we know that park use can be affected by whether you work, your health, and your exercise habits, we have a few questions about those. Please remember that your answers are anonymous.

26. Are you currently: (Check all that apply)

- Working full-time
 Working part-time
 Self-employed
 Unemployed, looking for work
 Retired
 Disabled
 A student (full or part time)
 A stay-at-home parent
 Other _____

27. What is your highest level of education completed?

(NOTE: If respondent attended school outside of the U.S. indicate the closest equivalent) (Check one)

- 6th grade or less
 7th-11th grade
 High school graduate or GED
 Some college (but no degree)
 Associate's degree (AA)
 Bachelor's degree (BA, BS)
 Some graduate school or graduate degree

28. How many times per week do you engage in physical activities such as walking, cycling or any activity that causes increased breathing or heart rate, leg fatigue, or causes you to perspire?

- 0 [skip to 30] 5
 1 6
 2 7 or more
 3 Don't know
 4

29. What is the usual length of these physical activities? (Check one)

- Less than 5 minutes
 > 5, but < 15 minutes
 15-30 minutes
 > 30, but < 45 minutes
 More than 45 minutes

30. Do you engage in physical activities as part of your work on a regular basis? (Check one)

- Yes No

31. How much time outside of work do you spend watching television, DVDs or videos, playing video games, or using a computer on an average day? (Check one)

- 0 - 60 minutes

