 - If no residential replacements are identified, note this on the Household Interview Log by writing “no replacement located” under the “Replacement address” column. If, however, a replacement address was determined, indicate the address on the log. It is also important to write in the reason for selecting an alternative address on the log.
2. Replace an **apartment** by selecting the first occupied unit to the **left** of the original unit. This scenario only applies IF the apartment identified when following the protocol outlined in the *Selecting Apartments* section yields an unoccupied unit (no people are currently residing in the unit).
 - a. If you come to the end of a hallway, return to the original unit and continue searching for an occupied unit to the right. If there are no occupied apartments on the same floor as the original unit, select the next highest floor, and so on. If no occupied units are identified, note this on the Household Interview Log by writing “no replacement located” under the “Replacement address” column. If a replacement address was determined, indicate the unit and floor number on the log. It is also important to write in the reason for selecting an alternative address on the log.
3. Replace a **freestanding unit** by selecting the first occupied unit encountered while walking beyond the originally unit. If no occupied units are identified, note this on the Household Interview Log by writing “no replacement located” under the “Replacement address” column. If a replacement address was determined, indicate the unit and floor number on the log. It is also important to write in the reason for selecting an alternative address on the log.

Selecting Interview Participants

When the appropriate residential address has been identified, knock on the door or ring the doorbell. When the door is answered, immediately explain who you are and why you are there. Proceed by asking to speak with the person who is **over 18, currently at home, with the next birthday**. Ask this person to participate in the interview process and notify her/him of the incentive. If this person declines, continue asking for participation until some agrees to participate or all people over the age of 18 refuse participation.

Attempted Interviews

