Make a total of four attempts to interview a person at each selected address. When returning to an address, always approach the same door as your initial attempt (e.g., front door or same apartment number). If no one answers the door, note the date AND time (e.g., AM or PM) next to the appropriate attempt check box in the “Attempts” column on the Household Interview Log.

If a minor answers the door and indicates there is no one over the age of 18 available, indicate the date AND time (e.g., AM or PM) next to the appropriate attempt check box in the “Attempts” column on the Household Interview Log. In the same space, indicate that a child was home by writing “minor only” above the date and time.

Conducting Interviews

For safety, always conduct surveys in the presence of another Interviewer. You should never enter a residence when talking with survey participants. Rather, conduct all interviews at the door. After you complete an interview, check the appropriate box in the “Outcome” column of the Household Interview Log to indicate that the person agreed to participate in the interview, and if it was conducted on the iPad or on a paper form. Note the date in the “Contact date” column.

Participants have the right to stop an interview at any time. If this happens, check the appropriate iPad or Paper box in the “Outcome” column and write “stopped” above the box that you checked in the “Outcome” column. Record the date as usual in the “Contact date” column.

Refusals

When residents (over age 18) indicate that they are unwilling to participate in the interview, note the refusal on the Household Interview Log by circling “Refusal” in the “Outcome” column. The date should be noted under the “Contact date” column.

When residents decline to participate, DO NOT attempt to conduct another interview at this address. Choose a replacement address from the alternatives provided.

No Contact

Each time you attempt contact at a residence you should circle the appropriate number in the “Attempts” column. If no contact was made with a resident (at least 18 years of age) after four attempts, make sure that each of the numbers is circled, and write “No contact” in the “Contact date” column.

Safety Considerations

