We used negative binomial distributions in the DID models due to the sizable heteroscedasticity in park use outcomes (Cohen et al., 2012). Effects of the intervention were presented in the scale of multiplicative scale (i.e., % changes) in these models. We also examined the outcomes by two age groups (youths versus adults). In analyzing survey outcomes, we controlled for respondent-level covariates to reduce estimation biases because randomization was not at the individual level, including gender, age, education level, obesity status, address buffer (<.25 mile, .25 to .5 miles, and .5 miles to 1 mile to park), self-rated health, perception of park safety, primary language, and having children under 18 years old. All statistical models were fitted in SAS 9.4. We also conducted sensitivity analyses using robust standard errors for park clustering effects and alternative scale for transformed mean outcomes (log or logit) wherever appropriate. The main findings were not sensitive to alternative model specifications.

Statistical power: This study was powered to detect a small to medium standard effect size under the regular setting of two-sided p -value <0.05 and power >0.80 . With 12 parks in each study arm and the extensive repeated measurements in each park (18 hourly observation per wave for two waves), we can detect a difference of 0.34 times standard deviation (SD) between any two arms when the intra-class correlation is no greater than 0.10. Based on historic data from previous studies (average park use 55 persons/hour, $SD=35$, approximately)(Cohen et al., 2013) meant that we could detect an additional 11.9 persons/hour. Because most survey outcomes were categorical, we used a two-sample z -test for calculating the detectable effect size for survey analysis. With 20 surveys in each wave and in each park's neighborhood, we could detect a difference of 15 percentage points for a binary outcome with a baseline prevalence between 20% and 80%. The detectable effect size is even smaller if the baseline prevalence rate is very high or very low (e.g. $<20\%$, or $>80\%$).

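### The SAP's survey-model covariates do not name employment, although household respondents are drawn only from adults at home and the questionnaire itself says work can affect park use

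*Protocol*

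**What the plan says.** The protocol describes a random sample of addresses (Participant Recruitment and Protection): "Household respondents are recruited using a random selection of residential addresses". Within the household, Appendix G (Selecting Interview Participants) gives the rule: "Proceed by asking to speak with the person who is over 18, currently at home, with the next birthday". On return visits the same appendix says: "Make a total of four attempts to interview a person at each selected address". The failed attempts it describes are no answer and a visit where only a minor is available.

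The questionnaire in Appendix C introduces its later items with this statement to the respondent: "Because we know that park use can be affected by whether you work, your health, and your exercise habits". Item 26 then records employment in nine categories, of which the respondent may tick several.

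The SAP (Data analyses) estimates intervention effects as the wave-by-arm interaction in difference-in-differences (DID) models. For survey outcomes it adds: "we controlled for respondent-level covariates to reduce estimation biases because randomization was not at the individual level". The list runs from gender, age, education, obesity status and address buffer through "self-rated health, perception of park safety, primary language, and having children under 18 years old". Employment is not named.

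**The concern.** The birthday draw makes the choice of respondent arbitrary only among the adults who happen to be in. An adult who is out at work is not in the draw once another adult answers the door, and nobody returns for that person. Presence at home plausibly depends on work, so the resident sample may hold too few workers.

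The two waves are separate cross-sections. The answers are anonymous and the monitoring plan says that no personal identifiers are held, so respondents cannot be linked across waves. Nothing in the documents fixes visiting hours or spreads attempts over times of day, so nothing in the design holds the employment mix constant from wave to wave.

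Of the three influences that the questionnaire names, health enters the SAP models as self-rated health, and exercise is a survey outcome. Work has no stated role. At stake are the survey results: visits in the past week, duration of visits, awareness of and participation in programs, perceived safety and weekly exercise sessions.

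**Working it through.** No figure in the plan is in dispute here. The calculations below give scale only, and every value marked as assumed is absent from the documents.

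**1. What the four attempts correct between addresses.** Assume one adult per address, 60% of adults employed, and a probability of being at home per visit of *h*₁ (employed) or *h*₀ (not employed). After *k* attempts, the employed share among those reached is

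0.6[1 − (1 − *h*₁)^*k*] / {0.6[1 − (1 − *h*₁)^*k*] + 0.4[1 − (1 − *h*₀)^*k*]}.

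| *h*₁, *h*₀ (assumed) | 1 attempt | 4 attempts | True share |
|---|---|---|---|
| 0.5, 0.7 | 52% | 59% | 60% |
| 0.3, 0.6 | 43% | 54% | 60% |
| 0.2, 0.7 | 30% | 47% | 60% |

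For the middle row, one attempt gives 0.18/(0.18 + 0.24) = 0.43, and four give 0.456/(0.456 + 0.390) = 0.54. The attempts remove part or most of the gap between addresses.

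**2. What they do not correct within a household.** Take two adults, one working and one not, with independent presence and the same assumed probabilities. At the first visit where an adult is reached, the worker is selected with probability

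[*h*₁(1 − *h*₀) + ½*h*₁*h*₀] / [1 − (1 − *h*₁)(1 − *h*₀)].

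- 0.5, 0.7: (0.15 + 0.175)/0.85 = 0.38
- 0.3, 0.6: (0.12 + 0.09)/0.72 = 0.29
- 0.2, 0.7: (0.06 + 0.07)/0.76 = 0.17

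A draw from all resident adults would give 0.50. The number of attempts does not enter the formula, because a return visit is made only when nobody eligible was reached.

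**3. What reaches the treatment effect.** Let *e* be the employed share in each arm-by-wave cell and *g* the outcome gap by employment. On the additive scale,

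bias in the DID = [(*e*_A2 − *e*_A1) − (*e*_B2 − *e*_B1)] × *g*.

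If selection is the same in both arms and both waves, the bracket is 0 and so is the bias. With an assumed differential shift of 5 to 20 points and a gap of 5 to 30 points, the bias runs from 0.05 × 0.05 = 0.25 percentage points to 0.20 × 0.30 = 6 percentage points. A middle case of 10 and 20 points gives 2. For comparison, the SAP puts its detectable difference for a binary survey outcome at 15 points.

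**4. What the covariate buys in precision.** The SAP's 12 parks per arm and 20 surveys per park and wave give 240 respondents per cell. Assume that half work, a gap of 1.0 visit per week and an outcome SD of 1.5 to 3 visits. Employment then accounts for 0.5 × 0.5 × 1.0² = 0.25 of a variance of 2.25 to 9. Adjustment shrinks the standard error by 1 − √(1 − 0.25/2.25) = 5.7% at most and 1 − √(1 − 0.25/9) = 1.4% at least, before allowing for clustering and for the covariates already in the model.

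**The case against.** The strongest reply is that one recruitment rule applies to every park, arm and wave, so stable selection cancels in the wave-by-arm contrast, and no passage points to a shift that differs by arm. That stands. A reader might infer that the at-home rule biases the survey effects. The documents do not show this; they show only that nothing would prevent it or adjust for it directly.

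A reader might also take chance imbalance as the size of the problem. With 240 per cell and an assumed 50% share, the DID in the working share has a standard error of √(4 × 0.25/240) = 6.5 points, so an imbalance of 10 points or more arises in about 12% of pairwise contrasts. This is ordinary sampling variation. It would be the same under a draw from all resident adults, and the model's standard error already reflects it. It says nothing about the at-home rule.

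To say that the sample is selected on working status also goes further than the text. The rule selects on presence at home. Visiting hours are not stated, park observation days include weekends, and station interviews may reach some people missed at home, although they are a convenience sample whose handling the SAP does not describe.

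The SAP says that all models carry fixed effects for time of day and for weekend versus weekday, and the questionnaire records interview time. If those terms apply to the survey models, they absorb part of any shift due to visiting hours. The wording speaks of observation times and may mean the park counts only, and in either case it does not adjust for employment itself. Age, gender, education, self-rated health and children under 18 plausibly track employment in part. The covariate list is introduced as a list of inclusions, so it may be incomplete, but nothing shows that employment was used.

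**Conclusion.** The point holds as a modest gap in the survey analysis. The within-household rule plausibly under-represents working adults in homes with several adults, by an amount that the documents do not allow anyone to estimate. Bias in a survey effect requires the employment mix to change differently by arm between waves. On the assumed ranges it would be 0.25 to 6 percentage points, and it is zero under stable selection. The expected gain from adjustment is a standard error smaller by roughly 1 to 6% under the assumptions shown, plus protection against a differential change in who was interviewed. The primary outcome (energy expenditure from park observation) and the secondary outcome (observed users) do not depend on the household sample.

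The case for the covariate rests on the plan's own reasoning: the questionnaire names work as an influence on park use, the item is recorded, and the SAP adjusts at respondent level in order to reduce bias.

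**What to change.** Add employment (working / not working, from item 26) to the respondent-level covariates in each survey model. State the grouping rule, because several boxes may be ticked; for example, count as working anyone who ticks full-time, part-time or self-employed, whatever else is ticked. Report employment by arm and wave, so that a reader can see whether the mix shifted. If employment was already in the models, say so in the SAP.

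The cost is one model term, a line in the SAP, one table and the loss or handling of records with item 26 missing. Park programs are unlikely to change employment, so adjustment should not remove part of the effect.

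Rewriting the Appendix G draw to cover all resident adults is not recommended here. It would need more return visits and could raise non-contact and reliance on station interviews. The SAP also reports the analyses in the past tense, so the change would come after fieldwork.

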Appendix K: Data and safety monitoring plan

Promoting Physical Activity in High Poverty Neighborhoods (HSPC Study ID: 2011-0692)

Data and Safety Monitoring Board

We have created a study DSMB that is external to the project staff to review all protocols and interim findings, including questionnaires, recruitment progress, interim data findings, and data quality. The DSMB will be composed of a statistician ([name], RAND), an expert in physical activity ([name], professor at San Diego State University) and an expert in parks and physical activity ([name], North Carolina State University).

The DSMB will monitor the overall conduct of the RCT and will ensure the overall safety of participants by protecting participants from avoidable harm and declaring clear benefit when there is proof beyond a reasonable doubt. The DSMB will meet at least once per year (or more as needed) by teleconference. If there are any adverse findings related to park improvements, these will be reported to the DSMB, our community partners (the Los Angeles Department of Recreation and Park, AltaMed Health Services), and the RAND HSPC. In addition, the DSMB will evaluate any adverse events (along with the HSPC) to protect the safety of study participants and study staff.

Data Monitoring Plan

Data Collection and Management

All data collected will not have any personal identifiers. Randomization is at the park level, rather than the person level. All datasets will be password-protected.

Quality control procedures will be utilized to ensure that park observations and recruitment is on schedule, treatment allocation is occurring as planned, data collection protocols are being used accurately.

A new quality control measure we would like to introduce is to take a photograph at one park target area during every observation. The photo will be time stamped and delivered with the data to RAND. Once received at RAND it will be deleted from the iPad mini. RAND staff will review the photo to validate the park user counts in that target area. Once it is reviewed by RAND, it will be stored in a password-protected file and will be deleted at the end of the study. It will be coded with the date, park ID number, and park target area.

Data Storage

Data will be collected by AltaMed Promotoras (field staff) on password-protected iPad minis and will be uploaded to Accellion. Computer files will be password-protected with restricted access to project staff. All analytic data files and databases will be maintained on a secure, password-protected server. iPad minis will have a password-protected ID known only to team members.

Data Transfer

Electronic data will be transferred from the iPad mini to RAND via Accellion. The data include the park observational data as well as the survey data (which do not contain any personal identifiers).

Elements of Safety Monitoring Plan

Reporting of Adverse Events

For this study, we will define an adverse event (AE) as any untoward physical or mental health occurrence that may present itself during the conduct of the study and that may or may not have a causal relationship with the study procedures.

For the baseline measurement, our greatest concern is the safety of the study staff that will be visiting parks in low income neighborhoods in pairs. They are trained to be careful and never to approach any person who appears intoxicated or mentally ill. If they see any illegal activity, such as drug deals, they are advised to leave the scene immediately. They are to carry cell phones and wear comfortable shoes.

We will use the FDA definition of serious adverse event (SAE), which is any adverse experience occurring during the intervention that results in any of the following outcomes: death, a life-threatening adverse experience, or a persistent or significant disability/incapacity.

Anticipated Adverse Events

1. Suicidal ideation or intent to harm self

Field Interviewers will not be probing for this information, since it is not part of the research task. However, if a study respondent spontaneously reports immediate intent to commit suicide, field interviews will follow procedures below:

Emergency – In the rare instance that a respondent is in imminent danger and needs emergency medical or mental health services, the Field Interviewer will insure her own safety and then will dial 911 on her cell phone and request assistance. If a respondent reports that they are thinking of committing suicide and has a plan to do so and then terminates the interview immediately after providing this information, this circumstance should be considered an emergency and the interviewer should dial 911 to request assistance. The Field Interviewer will immediately call the Project Coordinator and write and submit an incident report the same day.

The Project Coordinator will send an incident report to the RAND HSPC on the same day.

The Project Coordinator will consult with the RAND HSPC to determine whether further follow-up is needed.

Non-emergency –If a respondent spontaneously indicates that he/she is *thinking* about committing suicide (but has no immediate plan), the Field Interviewer will say:

“You seem to be having a difficult time. If you think this is an emergency, you can call 911 or another local emergency number such as the Mental Health Crisis Care [give 800 number]. If you think you need help with this problem, you can talk to your doctor, your therapist/counselor, or call a doctor/therapist in your area.”

The Field Interviewer will also provide the respondent with a written list of mental health referral numbers and suggest that he or she discuss feelings with their regular physician or with a mental health specialist obtained through referral. The Field Interviewer will call the Project Coordinator within one hour after the interview. The Field Interviewer will complete an incident report the same day.

The Project Coordinator will send the incident report to the RAND HSPC within 24 hours.

The Project Coordinator will consult with the RAND HSPC to determine whether further follow-up is needed.

2. Severe depression

The new survey instrument includes some questions about mental health. If the respondent appears to get very upset by these questions (either during or after the interview) and/or spontaneously discloses that they feel very depressed, the Field Interviewer will say:

“You seem to be having a difficult time. If you think this is an emergency, you can call 911 or another local emergency number such as the Mental Health Crisis Care [give 800 number]. If you think you need help with this problem, you can talk to your doctor, your therapist/counselor, or call a doctor/therapist in your area.”

The Field Interviewer will also provide the respondent with a written list of mental health referral numbers and suggest that he or she discuss feelings with their regular physician or with a mental health specialist obtained through referral. The Field Interviewer will call the Project Coordinator within one hour after the interview. The Field Interviewer will complete an incident report the same day.

3. Serious injury during physical activity class

Part of the intervention involves offering additional physical activity classes at select parks. We will be working closely with Park Directors in implementing these classes.

In addition, all activity instructors will administer verbal consent for participation in exercise classes in the parks, specifying that if potential participants have health concerns, or if they are over 60 and have never exercised before, they should talk to their doctor before participating in the classes.

All Activity Instructors will be trained on park procedures regarding in how to respond in the event that someone is injured or otherwise needs medical attention while participating in class. These include:

Emergency – In the rare instance that a respondent is in imminent danger and needs emergency medical services, the Activity Instructor will dial 911 on his or her cell phone and request assistance. The Instructor will also notify the Park Director (or park staff in charge if the Director is not there) and will notify the Project Coordinator and write and submit an incident report the same day.

The Project Coordinator will send an incident report to the RAND HSPC on the same day.

The Project Coordinator will consult with the RAND HSPC to determine whether further follow-up is needed.

Non-emergency – If a respondent is injured or becomes ill, but it is not an emergency, Activity Instructors will contact the Park Director (or park staff in charge if the Director is not there) and will notify the Project Coordinator and write and submit an incident report the same day.

The Project Coordinator will send the incident report to the RAND HSPC within 24 hours.

The Project Coordinator will consult with the RAND HSPC to determine whether further follow-up is needed.

